10.3 Investigational Product Handling

The Investigator and Research Pharmacist (if relevant) will be provided with Investigational Product Handling Guidelines that will provide details regarding the packaging and labeling requirements, receipt of investigational product, dispensing and accountability procedures, preparation instructions, storage and stability of the Investigational product and disposition of the Investigational Product.

| | |
|---|---|
| Exalenz Bioscience Ltd. | Last update: February 20, 2018 |
| Study Title: Companion protocol for the ¹³C-Methacetin Breath Test (MBT) for use in Bristol-Myers Squibb phase 2b studies for BMS-986036 (PEG-FGF21), under Protocols MB130-068 and MB130-069 | Protocol: BMS-EX-0118 Version: 1.0 |
| Document No: CSP000002 | Page 36 of 38 |

10.4 Investigational Product Accountability

The Investigator and Study Pharmacist (if relevant) are responsible for ensuring that all study supplies received at the site are inventoried and accounted for throughout the study. The dispensing of study substrate to the subject must be documented in the respective accountability form. The study Investigational Product must be stored in a limited access area or in a locked cabinet under appropriate environmental conditions. Unused study materials must be available for verification by the sponsor's site monitor during on-site monitoring. The destruction of unused study materials (both, expired or unexpired) will be documented on the return/disposition form. The Sponsor will authorize destruction of excess supplies on site according to local policy or arrange collection of unused supplies. In the case of local destruction, before proceeding, the site must seek authorization from the Sponsor using the return/destruction form and this must also be documented on the Study Supply Return Form.

Study substrate should be dispensed under the supervision of the investigator, a qualified member of the investigational staff, or by hospital clinical pharmacist.

11 ETHICS & REGULATORY CONSIDERATIONS

The protocol will be conducted in the US and Japan by BMS as Phase 2b studies of BMS-986036, MB130-068 and MB130-069. As such, regulatory requirements that are relevant for pharmaceutical investigations in US and Japan that will be applicable during the studies are to be conducted and overseen by BMS.

BMS will obtain for the main study an IND (IND-125297) and the applicable regulatory approvals for the MBT sub-study and the use of clinical data from all regulatory authorities (if relevant) and ethics committees/IRBs.

12 SAFETY CONSIDERATIONS

All adverse events (AE), serious adverse events (SAE), suspected unexpected serious adverse reactions (SUSAR) and unanticipated adverse device effects (UADE) possibly or probably related to the use of the MBT product or related to the MBT procedure will be collected and reported according to local regulations.

Safety assessments of the BMS study drug (BMS-986036) will be performed as described in BMS protocols MB130-068 and MB130-069.

| | |
|---|---|
| Exalenz Bioscience Ltd. | Last update: February 20, 2018 |
| Study Title: Companion protocol for the ¹³C-Methacetin Breath Test (MBT) for use in Bristol-Myers Squibb phase 2b studies for BMS-986036 (PEG-FGF21), under Protocols MB130-068 and MB130-069 | Protocol: BMS-EX-0118 Version: 1.0 |
| Document No: CSP000002 | Page 37 of 38 |

13 SUBJECT CONFIDENTIALITY

The subject's name and personal data will remain confidential and will not be published in any way. All data will be coded and stored in locked offices or on password protected computers.

14 MONITORING AND QUALITY ASSURANCE

This study is a companion protocol that will use the data generated by the BMS Phase 2b studies of BMS-986036, under protocols MB130-068 and MB130-069. BMS will ensure compliance with GCP, local regulations and scientific integrity and will manage and oversee the study conduct.

15 PUBLICATION POLICY AND FINANCE

It is intended that the results of the companion study will be reported and disseminated at international conferences and in peer-reviewed scientific journals. The policy regarding publications appears in the non-disclosure agreement signed by each study participant prior to signing of the contract.

16 FINANCIAL ASPECTS

The BreathID® MCS device and test kit including a nasal cannula and a solution containing ¹³C-Methacetin will be provided by Exalenz Bioscience. BMS will be responsible for the funding of regulatory approvals in regards to their main protocols and administration as well as for the funding for study support of staff at local sites.

17 STUDY TERMINATION

This study is a companion protocol that will use the data generated by BMS from its Phase 2b studies of BMS-986036 under protocols MB130-068 and MB130-069. BMS will be responsible for study termination procedures, when applicable.

1 ABBREVIATIONS

AE	- Adverse Event
cDOB	- Cumulative Delta over Baseline
CI	- Confidence Interval
CL	- Confidence Limits
CO ₂	- Carbon dioxide
cPDRxx	- Cumulative Percentage Dose Recovery at xx minutes from ingestion
CRF	- Case Report Form
CSR	- Clinical Study Report
CTP	- Child-Turcotte-Pugh (score)
DOB	- Delta over Baseline
DXA	- Dual-Energy X-Ray Absorptiometry
EA	- Efficacy Analysis (set)
eCRF	- Electronic Case Report Form
GCP	- Good Clinical Practice
HCC	- Hepatocellular Carcinoma
HE	- Hepatic Encephalopathy
HR	- Hazard Ratio
IRT	- Interactive Response Technology
ITT	- Intent to treat (population)
MBT	- ¹³ C-Methacetin Breath Test
MCS	- Molecular Correlation Spectrometry
MELD	- Model for Endstage Liver Disease
mEA	- modified Efficacy Analysis (set)
MMRM	- Mixed Effect Repeated Measures (Model)
NAFLD	- Nonalcoholic Fatty Liver Disease
NASH	- Nonalcoholic Steatohepatitis
PDR	- Percent Dose Recovery rate (expressed as % per hour)
PDR _{peak}	- Maximal Percent Dose Recovery rate
PP	- Per Protocol (analysis set)
PTFU	- Post-Trial Follow-Up
QW	- One per week
SA	- Safety Analysis (set)

Meridian Bioscience Israel Ltd.	Last update: May 05, 2021
SAP for Protocol BMS-EX-0118: Companion protocol for the ¹³C-Methacetin Breath Test (MBT) for use in Bristol-Myers Squibb phase 2b studies for BMS-986036 (PEG-FGF21), under Protocols MB130-068 and MB130-069	Document Version: 1.0
Document Nº: CSD00114	Page 6 of 21

SAE	- Serious Adverse Event
SAP	- Statistical Analysis Plan
SBP	- Spontaneous Bacterial Peritonitis
SD	- Standard Deviation
SDV	- Source Data Verification
SF	- Screen Failures
SUSAR	- Suspected unexpected serious adverse reaction
UADE	- Unanticipated Adverse Device Effect
US	- United States (of America)
USA	- United States of America

Meridian Bioscience Israel Ltd.	Last update: May 05, 2021
SAP for Protocol BMS-EX-0118: Companion protocol for the ¹³C-Methacetin Breath Test (MBT) for use in Bristol-Myers Squibb phase 2b studies for BMS-986036 (PEG-FGF21), under Protocols MB130-068 and MB130-069	Document Version: 1.0
Document Nº: CSD00114	Page 7 of 21

2 INTRODUCTION

This Statistical Analysis Plan (SAP) was developed based on the original companion study protocol BMS-EX-0118 version 1.0, dated 20 February 2018, titled “Companion Protocol for the ¹³C-Methacetin Breath Test (MBT) for use in Bristol-Myers Squibb phase 2b studies for BMS-986036 (PEG-FGF21), under Protocols MB130-068 and MB130-069”. This SAP is an updated and more detailed companion to the “Statistical Methods” section of the original companion study protocol.

The original protocol and most of the study documents were written and maintained by Exalenz Bioscience Ltd. before being acquired by and integrated into Meridian Bioscience, Inc., and renamed Meridian Bioscience Israel Ltd. Therefore “Meridian” and “Exalenz” can be referred to as interchangeable terms in this SAP.

The companion protocol and this SAP describe how Exalenz intends to use the clinical data being obtained during the studies conducted by BMS sponsored IND studies: MB130-068 and MB130-069. The data collected as part of MB130-068 will be referred to as ‘cohort 1’ and the data collected as part of MB130-069 will be referred to as ‘cohort 2’.

The enrollment phase and all MBT testing (incl. Day1, Week 24 and Week 48 visits) for the aforementioned BMS sponsored studies has been completed. The data is still being reviewed by BMS and the respective databases are planned to be made available to Exalenz between July and November 2021, after their respective data lock and release from BMS.

The initially planned sample size of 250 subjects, per statistical section in the companion protocol, was not reached for multiple reasons:

- The MBT testing as part of the BMS studies, was an opt in substudy, requiring an additional consent process. Subjects enrolled to the BMS studies were reluctant to add an additional investigational test to their study schedule.
- The COVID-19 outbreak further complicated the enrollment and especially the follow up testing of already enrolled subjects, as visits were more and more conducted remotely and any breath testing was avoided during in person visits.

Since the actual final sample size of subjects with valid MBT results at baseline and post-treatment phase, across both BMS studies, is expected to be lower than 80, the statistical analyses

Meridian Bioscience Israel Ltd.	Last update: May 05, 2021
SAP for Protocol BMS-EX-0118: Companion protocol for the ¹³C-Methacetin Breath Test (MBT) for use in Bristol-Myers Squibb phase 2b studies for BMS-986036 (PEG-FGF21), under Protocols MB130-068 and MB130-069	Document Version: 1.0
Document Nº: CSD00114	Page 8 of 21

for the study will be descriptive by nature. No formal statistical testing will be performed. Nominal p-values from statistical tests will be reported for supplementary information.

When differences exist in methods, descriptions or explanations provided in the protocol and this SAP, the SAP prevails.

Since this study is a companion to a pharmaceutical company's study, the data management for the main study can independently determine as to when a data freeze or a data lock shall be performed. Therefore, for the Exalenz companion protocol purposes, any amendments to the SAP will be made prior to Exalenz independently accessing the data from the database freeze or lock, if available. In case additional analyses not described in the final SAP or deviations from the final SAP are required, they will be documented in the Clinical Study Report (CSR).

3 STUDY OBJECTIVES AND ENDPOINTS

3.1 *Study Objectives*

3.1.1 *Primary Objective*

The data generated in this companion study will be used to demonstrate the ability of the MBT to evaluate patient response to treatment with BMS-986036, comparing placebo to each treatment arm individually. Primary efficacy assessment will be performed using the Week 24 and the Week 48 visit measures compared to Day 1 (change from baseline) for the combined population of the two cohorts, according to availability, by dose of the BMS drug under study.

The same assessments for each study cohort independently will be reported.

3.1.2 *Secondary Objective*

The following assessments will be done by treatment arm by dose of the BMS drug under clinical investigation and combined arms on the combined population of the two study cohorts:

1. To demonstrate the short and long-term prognostic value (3 months, 6 months and 1 year, respectively) of MBT for liver disease deterioration (reported as liver-related

Meridian Bioscience Israel Ltd.	Last update: May 05, 2021
SAP for Protocol BMS-EX-0118: Companion protocol for the ¹³C-Methacetin Breath Test (MBT) for use in Bristol-Myers Squibb phase 2b studies for BMS-986036 (PEG-FGF21), under Protocols MB130-068 and MB130-069	Document Version: 1.0
Document Nº: CSD00114	Page 9 of 21

clinical outcome events). Assessment will be performed using MBT from the Day 1, Week 24 and Week 48 visits.

2. To assess the ability of changes in the MBT to reflect biopsy proven changes in fibrosis and/or NAS as assessed by a central reader, where available, at Week 24 (or at least Week 20 in cases of an Early Termination time point) (for cohort 1) or at Week 48 (for cohort 2) compared to the baseline biopsy from the screening visit.
3. To assess the ability of changes in the MBT to reflect changes in liver stiffness as measured by Magnetic Resonance Elastography (MRE), where available, at Week 24 and Week 48 (or at Early Termination) compared to baseline MRE from the screening visit.
4. To assess the ability of changes in the MBT to reflect changes in Proton Density Fat Fraction (PDFF) as measured by Magnetic Resonance Imaging (MRI), where available, at Week 24 and Week 48 (or Early Termination), compared to baseline MRI from the screening visit.
5. To assess the ability of changes in the MBT to reflect changes in Serum Pro-C3, where available, at Week 24 and Week 48 of treatment (or Early Termination), compared to baseline Pro-C3 from the screening visit.

The same assessments for each study cohort independently will be reported.

The following additional objectives are applicable for cohort 2 only:

1. To assess the ability of changes in the MBT to reflect changes in liver stiffness as measured by “Fibroscan” elastography, where available, at the Week 48 visit (or earlier if there was an Early Termination) compared to the screening visit.
2. To assess the ability of changes in the MBT to reflect changes in the Model for End-stage Liver Disease (MELD) score, where available, at Week 24 and Week 48 visits compared to study Day 1.
3. To assess the ability of changes in the MBT to reflect changes in the Child-Turcotte-Pugh Scoring (CTP) score, where available, at Week 24 and Week 48 (or Early Termination) compared to study Day 1.

Meridian Bioscience Israel Ltd.	Last update: May 05, 2021 Document Version: 1.0
SAP for Protocol BMS-EX-0118: Companion protocol for the ¹³C-Methacetin Breath Test (MBT) for use in Bristol-Myers Squibb phase 2b studies for BMS-986036 (PEG-FGF21), under Protocols MB130-068 and MB130-069	
Document Nº: CSD00114	Page 10 of 21

3.1.3 *Exploratory Objective*

- To assess the ability of the MBT to monitor patient status in comparison to other available measures, such as Liver Fibrosis stage, NAS, MELD, CTP, PDFF, Liver Stiffness, Serum Biomarker or Pro-C3.

3.1.4 *Safety Objective*

Evaluation of safety related to the MBT.

3.2 *Study Endpoints*

3.2.1 *Primary Endpoint*

The MBT's ability to measure the effect of BMS-986036 treatment on the metabolic capacity of the liver at Week 24 and Week 48 visits during the Double-Blind Treatment Period, as compared to changes in placebo treated subjects.

3.2.2 *Secondary Endpoints*

In order to assess the correlation of changes in MBT with changes in other measures of liver disease, the following endpoint measures will be collected, where available:

For all study cohorts: MBT results for each MBT visit (Day 1, Week 24, Week 48, or Early Termination visits) as well as changes in MBT results (cPDR₃₀, PDR_{peak} or other breath test parameters).

The other measures of liver disease that will also be collected in this study are as follows:

1. Liver-related Clinical Outcome defined as the first occurrence of any one of the following: all-cause mortality, MELD score ≥ 15 , liver transplant, hepatocellular carcinoma (HCC), ascites requiring medical intervention, hospitalization (≥ 24 hours) for onset of variceal bleeding, hepatic encephalopathy and spontaneous bacterial peritonitis.
2. Liver Fibrosis stage and NAS as determined by Liver Biopsy assessed by a central reader.
3. Liver Stiffness as determined by MRE.
4. PDFF as determined by MRI.
5. Serum Biomarker Pro-C3.

Meridian Bioscience Israel Ltd.	Last update: May 05, 2021
SAP for Protocol BMS-EX-0118: Companion protocol for the ¹³C-Methacetin Breath Test (MBT) for use in Bristol-Myers Squibb phase 2b studies for BMS-986036 (PEG-FGF21), under Protocols MB130-068 and MB130-069	Document Version: 1.0
Document Nº: CSD00114	Page 11 of 21

Additional measures for cohort 2 include:

1. Liver Stiffness as determined by Fibroscan® Elastography
2. MELD scores
3. CTP scores

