7.2 Secondary Efficacy Objectives

The following assessments will be done by treatment arm and combined arms for each study cohort independently, according to availability, and on the combined population of the two study cohorts by dose of the BMS drug under study:

1. To demonstrate the short and long-term prognostic value (3 months, 6 months and 1 year, respectively) of MBT for liver disease deterioration (reported as liver-related clinical outcome events). Assessment will be performed using MBT from the day 1, and 24 and 48 week visits.
2. To assess the ability of changes in the MBT to reflect biopsy proven changes in fibrosis and/or NAS as assessed by a central reader at week 24 (or at least week 20 in cases of an early termination time point) (for cohort 1) or at week 48 (for cohort 2) compared to the baseline biopsy from the screening visit.
3. To assess the ability of changes in the MBT to reflect changes in liver stiffness as measured by Magnetic Resonance Elastography (MRE) where available at weeks 24 and 48 (or at early termination) compared to baseline MRE from the screening visit.
4. To assess the ability of changes in the MBT to reflect changes in Proton Density Fat Fraction (PDFF) as measured by Magnetic Resonance Imaging (MRI) where available - at weeks 24 and 48 (or early termination), compared to baseline MRI from the screening visit.
5. To assess the ability of changes in the MBT to reflect changes in Serum Pro-C3 at 24 and 48 weeks of treatment (or early termination), compared to baseline Pro-C3 from the screening visit.

| | |
|---|---|
| Exalenz Bioscience Ltd. | Last update: February 20, 2018 |
| Study Title: Companion protocol for the ¹³C-Methacetin Breath Test (MBT) for use in Bristol-Myers Squibb phase 2b studies for BMS-986036 (PEG-FGF21), under Protocols MB130-068 and MB130-069 | Protocol: BMS-EX-0118 Version: 1.0 |
| Document No: CSP000002 | Page 21 of 38 |

The following additional objectives are applicable for cohort 2 only:

1. To assess the ability of changes in the MBT to reflect changes in liver stiffness as measured by "Fibroscan" elastography at the 48 week visit (or earlier if there was an early termination) compared to the screening visit.
2. To assess the ability of changes in the MBT to reflect changes in the Model for End-stage Liver Disease (MELD) score at 24 and 48 week visits compared to study day 1.

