7.7 Efficacy Variables

Study procedures and timing are summarized in the Schedule of Events of protocols MB130-068 and MB130-069.

The following procedures or tools will be used to assess subjects' disease activity during the study:

- MBT at selected sites in subjects who opt in at Day 1, week 24 and week 48.
- Liver biopsy at Screening (if no biopsy is available from within 6 months of the Screening Visit), week 24 (for subjects in protocol MB130-068/cohort 1) or week 48 (for subjects in protocol MB130-069/cohort 2)
 - Histological assessments of fibrosis stage and NASH activity (NAS)
- Liver stiffness as determined by MRE at selected sites at screening, week 24 and week 48
- Hepatic fat fraction as determined by MRI at selected sites at screening, week 24 and week 48.
- Serum Biomarker Pro-C3 at Screening, Day 1, week 24, week 48 and week 52.

Additional variables for cohort 2:

- Fibroscan® elastography at Screening and week 48 or early termination
- MELD Scores at Screening, Day 1, every 4 weeks up to week 24, every 8 weeks up to week 48 and week 52.

| | |
|---|---|
| Exalenz Bioscience Ltd. | Last update: February 20, 2018 |
| Study Title: Companion protocol for the ¹³C-Methacetin Breath Test (MBT) for use in Bristol-Myers Squibb phase 2b studies for BMS-986036 (PEG-FGF21), under Protocols MB130-068 and MB130-069 | Protocol: BMS-EX-0118 Version: 1.0 |
| Document No: CSP000002 | Page 23 of 38 |

- Child-Pugh scores at Screening, Day 1, every 4 weeks up to week 24 and every 8 weeks up to week 48 and week 52.
- Liver-related Clinical outcome events at each visit from Day 1 through week 52 and during the Long-Term Bone Mineral Density and Immunogenicity Follow-Up Period (up to 14 Months after week 52).

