7.7.8 Child-Turcotte-Pugh (CTP) Scoring

The Child-Turcotte-Pugh (CTP) score assesses the severity of cirrhosis and will be done for cohort 2 Subjects. It has been shown to be an accurate measure across a broad spectrum of liver disease. It employs numerical scores of 5 measures of liver disease: total bilirubin, serum albumin, international normalized ratio for INR, ascites, and encephalopathy and is scored according to the scheme in Appendix 8 of study protocols MB130-068 and MB130-069. The sum of scores from each component is the final score.

Blood samples will be collected for the total bilirubin, serum albumin, and prothrombin time assessments used to calculate the CTP score as part of the hematology and serum chemistry assessments conducted at each visit. The same central laboratory will be used for each evaluation. Evaluations of ascites and encephalopathy are to be conducted by the same site personnel at each visit wherever possible.

CTP scores will be determined at each study visit.

7.7.9 ¹³C-Methacetin Breath Test (MBT)

The ¹³C-Methacetin Breath Test (MBT) is a non-invasive tool that provides an estimate of liver function by assessing microsomal capacity to metabolize the non-radioactive ¹³C-labeled Methacetin. MBT measures carbon dioxide exhaled into a nasal cannula before and after drinking a non-radioactive solution (called ¹³C-methacetin), using a device called the BreathID® MCS device. The amount of ¹³carbon dioxide (¹³CO₂) exhaled over 60-85 minutes will then be measured. The MBT, which consists of both a device and an unapproved drug component, is considered an investigational device that has not been reviewed, approved or cleared by the FDA for marketing purposes.

In Subjects evaluated/listed for liver transplantation, a reduction in exhaled ¹³CO₂ has been associated with an increased risk of cirrhotic complications ⁽³⁾. MBT will be conducted at selected sites in subjects who provide consent. The test will be performed after an 8-hour fast according to study guidelines and as per the manufacturer's instructions.

MBT will be conducted at Day 1 visit prior to first dose of treatment, week 24 and week 48. For participants discontinuing study treatment at sites selected for the MBT sub-study, MBT should be conducted only if the date of discontinuation is more than 12 weeks from the date of the previous MBT.

| | |
|---|---|
| Exalenz Bioscience Ltd. | Last update: February 20, 2018 |

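### Pro-C3 change is measured from Screening while MBT change starts at Day 1, although a Day 1 Pro-C3 sample is listed

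*SAP*

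**What the plan says.** **Pro-C3.** SAP 3.1.2 item 5 takes the change "at Week 24 and Week 48 of treatment (or Early Termination), compared to baseline Pro-C3 from the screening visit". Protocol 7.2 item 5 has the same reference, "at 24 and 48 weeks of treatment (or early termination), compared to baseline Pro-C3 from the screening visit", as does the synopsis.

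**MBT.** Protocol 7.7.9 states "MBT will be conducted at Day 1 visit prior to first dose of treatment, week 24 and week 48". No screening MBT is planned. SAP 8.4.2.2 measures MBT change from baseline, which under SAP 8.2 is Day 1.

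**Sampling.** Protocol 7.7 lists "Serum Biomarker Pro-C3 at Screening, Day 1, week 24, week 48 and week 52". Protocol 7.7.6 gives a different Pro-C3 visit list (weeks 4, 8, 12, 24, 48 and 52) with neither Screening nor Day 1, though it also says biomarker blood is taken at every visit.

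**MELD and CTP (cohort 2).** Both are listed at Screening and Day 1: "MELD Scores at Screening, Day 1, every 4 weeks up to week 24" and "Child-Pugh scores at Screening, Day 1, every 4 weeks up to week 24". SAP 3.1.2 takes MELD change "at Week 24 and Week 48 visits compared to study Day 1" and CTP change "at Week 24 and Week 48 (or Early Termination) compared to study Day 1".

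**General baseline rules.** Protocol 9.6.1 uses the last valid value before treatment starts. SAP 8.2 defaults to Day 1 unless another baseline is specified. SAP 8.4.2.2, which describes the correlation analysis, refers to change from baseline without naming a visit for Pro-C3.

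**The concern.** The secondary analysis asks whether MBT change tracks Pro-C3 change. As item 5 reads, the Pro-C3 score includes whatever happens between Screening and Day 1, before any study drug, and the MBT score does not. If Pro-C3 moves in that interval independently of later change, the movement is noise in one of the two variables and pulls the change–change correlation towards zero.

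Pro-C3 is the only comparator listed at both visits that is not anchored at Day 1, and neither document gives a reason. For biopsy, MRE, PDFF and Fibroscan no Day 1 value is listed, and the biopsy may predate Screening by up to 6 months. Alignment at Day 1 is therefore not available for those four.

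The primary responder analysis is unaffected, as are the Week 24 to Week 48 changes, which use no baseline.

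**Working it through.** The documents give no correlation, variance or power for this analysis, so there is no planned figure to reproduce. The check covers which baseline applies, the window lengths, and the possible effect under stated assumptions.

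**1. Which baseline applies.** SAP 8.2 allows exceptions to Day 1, and item 5 names Screening explicitly. Reading item 5 as such an exception carries Screening into SAP 8.4.2.2. That is the natural reading, but 8.4.2.2 does not say so. An analyst working only from 8.2 and 8.4.2.2 could use Day 1.

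**2. Window lengths.** Let T be the weeks from Day 1 to the visit (24 or 48) and L the weeks from the screening draw to Day 1. Protocol 5 gives a 4 to 8-week screening period and Protocol 8.1 up to 8 weeks. The draw date within screening is not given, so L is taken as 0 to about 8. The excess of the Pro-C3 window is L/T:
- Week 24: 0 to 8/24 = 33.3%
- Week 48: 0 to 8/48 = 16.7%

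**3. Effect on the correlation (assumed models).** The multiplier is the Screening-based correlation divided by the Day 1-based one.

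*(a) Random walk, pre-dose drift independent of later Pro-C3 and MBT change, no assay error.* Covariance with MBT is unchanged and Pro-C3 variance grows from T to T+L, so the multiplier is √(T/(T+L)).

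| L (weeks) | T = 24 | T = 48 |
|---|---|---|
| 1 | √(24/25) = 0.980 | √(48/49) = 0.990 |
| 4 | √(24/28) = 0.926 | √(48/52) = 0.961 |
| 8 | √(24/32) = 0.866 | √(48/56) = 0.926 |

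*(b) As (a), but half the Day 1-based change variance is assay error.* Variance goes from 2T to 2T+L, so the multiplier is √(2/(2+L/T)). For L = 8: √(2/2.333) = 0.926 at Week 24 and √(2/2.167) = 0.961 at Week 48.

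*(c) No pre-dose drift, no change in error.* Multiplier 1.00.

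*(d) Subject-specific linear slopes, common gap.* Screening-based change equals Day 1-based change times (T+L)/T, a constant, so the multiplier is 1.00. If gaps instead vary uniformly over 0–8 weeks, independently of zero-mean slopes, let k = 1 + L/24. Then mean k = 1.1667, var k = (64/12)/576 = 0.0093, and the multiplier is 1.1667/√(1.3611 + 0.0093) = 0.997.

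*(e) Drift correlated c with later Pro-C3 change, variances proportional to time, drift related to MBT only through later Pro-C3 change.* The multiplier is (√T + c√L)/√(T + L + 2c√(TL)). For T = 24, L = 8:
- c = −0.5: (4.899 − 1.414)/√(32 − 13.856) = 0.818
- c = 0: 0.866
- c = +0.5: (4.899 + 1.414)/√(32 + 13.856) = 0.932

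**4. Size against sampling error.** SAP 2 expects fewer than 80 subjects with valid baseline and post-treatment MBT, so n = 79 is the most favourable case. For an assumed r = 0.30, Fisher z = 0.3095 with standard error 1/√76 = 0.1147, giving a 95% interval of 0.08 to 0.49. At 20 per arm (assumed equal split), the standard error is 1/√17 = 0.2425 and the interval is −0.16 to 0.66. The 8-week, Week 24 case under (a) turns 0.30 into 0.30 × 0.866 = 0.26, well inside either interval.

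**The case against.** The Screening reference is a consistent choice. It appears in the synopsis, Protocol 7.2 and SAP 3.1.2, and it puts Pro-C3 with biopsy, MRE, PDFF and Fibroscan. A common pre-treatment reference for those measures can be defended. That is fair, and it is why this is a question of better design and not an error. But Pro-C3 is correlated with MBT, not with the other comparators, so alignment with MBT matters more.

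The Day 1 value may not exist. Protocol 7.7 refers timing to the parent schedules, Protocol 7.7.6 omits Day 1, a blood draw is not an assay, and nothing states that the Day 1 sample precedes dosing. This stands as a condition on the fix. It does not favour Screening, which 7.7.6 omits as well.

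SAP 8.4.2.2 does not itself impose Screening, so the firmest defect may be an unnamed visit. This also stands. It supports naming the visit there whichever one is chosen.

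No loss is demonstrated. The multipliers run from 0.82 to 1.00 depending on the assumed model, and the analysis is secondary, descriptive and limited to subjects with data. That is correct, and it limits the weight of the point. It does not make Screening the better reference when a Day 1 value is listed.

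**Conclusion.** The concern holds as a minor design point. Read as written, the plan pairs a Pro-C3 change from Screening with an MBT change from Day 1. The protocol lists a sample that would align them, and both the protocol's general baseline rule (if that sample was drawn before dosing) and the SAP's default point to it.

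The extra Pro-C3 window is 0–33% at Week 24 and 0–17% at Week 48, given a gap of 0 to 8 weeks. The effect on the correlation cannot be bounded from the documents. It ranges from none (no drift, or linear slopes with a common gap) to a factor of about 0.87 at Week 24 under independent random-walk drift over 8 weeks, and 0.82 if that drift is negatively correlated with later change. A fall from 0.30 to 0.26 would not by itself alter interpretation at the expected sample size. Exposure is confined to the change-from-baseline correlations for one of seven comparators. Confidence is medium, because the Day 1 assay is unconfirmed and the drift models are assumed.

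**What to change.** 1. Confirm from the parent-study schedules that Pro-C3 was assayed at Day 1 and drawn before dosing.
2. If so, define Pro-C3 baseline in SAP 3.1.2 item 5 and SAP 8.4.2.2 as the Day 1 pre-dose value, with Screening used only where Day 1 is missing. Report how many subjects rely on the fallback, since it mixes reference visits.
3. State that this departs from Protocol 7.2 item 5 and that the SAP takes precedence, as SAP 2 provides.
4. Keep the Screening-based change as a sensitivity analysis, so that the protocol's stated objective is still reported.
5. If Day 1 Pro-C3 is unavailable, keep Screening and name that visit in SAP 8.4.2.2.

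The cost is one or two SAP sentences and one extra sensitivity run. SAP 2 allows amendment before the sponsor accesses the data. No new samples are needed if Protocol 7.7 reflects practice. The downside is a small departure from the protocol's wording and dependence on Day 1 availability.
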